## **Outcomes and Efficacy of Ejaculatory Preserving Transurethral Resection of Prostate**

**NCT05914519**

**Date 15/10/2025**

### **Introduction:**

The prostatic gland plays a central role in andrology. It is involved both in fertility and in sexuality with a major role in ejaculation and possibly in orgasm. This could explain the association between the andrological symptoms and prostatic disorders [1].

The prevalence of Benign Prostatic Hyperplasia (BPH) is approximately 50% for men in their fifties and reaches up to 80% for men over 80 years of age, representing one of the most common diseases affecting males, with potentially significant impact on their quality of life [2].

It is estimated that around half of men suffering severe or medical treatment unresponsive lower urinary tract symptoms (LUTS) will be offered a surgical procedure to relieve benign prostatic obstruction (BPO) [3].

Despite continuing development of new minimally invasive surgical methods, transurethral resection of the prostate (TURP) still remains the gold standard surgical treatment for LUTS due to BPH [4, 5].

Although it is benign, this disease has been shown to have a negative impact on the patient's health-related quality of life (HRQL), marked by obstructive and irritative LUTS [6, 7].

As BPH in most cases is not a life-threatening condition, the main outcomes of its treatment are not only the improvement in LUTS and functional parameters but also quality of life after surgery [8].

Whilst efficacy of the conventional TURP is proven, a common potentially bothersome side effect, the retrograde ejaculation (RE) which occurs in 65–90% of patients undergoing TURP [9].

It has been reported that ablative techniques like TURP and recent laser procedures including holmium, thulium and greenlight cause similar rates of ejaculatory dysfunction, occurring in almost three out of four to five men [10].

For decades, men have been counseled to expect dry orgasm after TURP because of the retrograde flow of semen as a result of bladder neck disruption [11].

Erectile dysfunction and Ejaculatory dysfunction (EjD) can have a substantial deleterious effect on the Quality of life (QoL) of men who have previously maintained regular sexual activity, inducing significantly increased levels of anxiety and depression [12].

More recently, a better understanding of ejaculation physiology has enabled the emergence of modified surgical techniques with the aim of preserving antegrade ejaculation [13–16].

The key point of standard TURP is resecting the tissues enveloped in the prostatic capsule and the bladder neck, while protecting the urethral tissues below the verumontanum [17].

The bladder neck plays a significant role in reproduction. For men, bladder neck closure facilitates anterograde ejaculation. It actively contracts the bladder neck during ejaculation through a rich noradrenergic innervation by sympathetic nerves [18].

Vernet et al. showed that contraction of the bladder neck was not important for anterograde ejaculation [19]. Using endorectal ultrasound videos performed during masturbation in 30 men, it was possible to visualize the bladder neck, the prostate, and the bulbar urethra during ejaculation. They observed that during ejaculation, the verumontanum underwent a slight

caudal shift, momentarily making contact with the opposite urethral wall and sperm emitted from the ejaculatory ducts was directed distally by contractions of the external sphincter coordinated with contractions of the bulbar urethra, thus demonstrating the importance of the muscular tissue around the verumontanum and particularly its proximal part. They described this area as a “high-pressure ejaculatory area”. The closure of the bladder neck did not seem to play a role in this mechanism. As a result, one can conclude that as long as the tissues around the verumontanum are not injured, ejaculation should still occur even with a well-open bladder neck [20].

Recently, together with a better understanding of the mechanisms of ejaculation, a greater importance has been given to the impact of dry ejaculation on patients’ QoL [21]. A balance between symptomatic improvement in LUTS and preservation of sexual function needs to be addressed for men seeking surgical treatment [22].

Modifications based on Supramontanal sparing hypothesis have reported favorable outcomes to as high as 92% [23].

Although preservation of bladder neck structures is often associated with preservation of antegrade ejaculation, the current modern approach is the preservation of the precollicular and para-collicular tissue in the area where the ejaculatory ducts emerge near the verumontanum in the distal apical tissue in laser, aquablation, and bipolar electrosurgical prostatectomy techniques [24].

### **Aim of the work:**

The purpose of this study is to assess the outcomes and efficacy of ejaculatory preserving TURP in terms of voiding, erectile function, and ejaculation.

### **Patients and method:**

**-Place of the study:**

Sohag university hospital, Urology department.

**-Type of the study:**

A prospective comparative study.

**-Study Population:**

The study will be carried out between July 2023 and January 2025. All patients who are eligible for inclusion will be picked up from Sohag University Hospital's urology outpatient clinic and will undergo TURP. They will be assigned to two groups.

**-Patients:**

**-Inclusion criteria:**

Adult patient  $> 45$  years old.

Men with drug refractory urinary retention.

Prostate volume range: 20–60 mL.

The International Prostate Symptom Score (IPSS)  $> 19$  after the medical therapy failure.

Maximum urinary flow rate (Qmax)  $< 10$  mL/s.

Serum prostate-specific antigen (PSA)  $< 4$  ng/mL with biopsy proven BPH if serum PSA  $> 4$  ng/mL or abnormal digital rectal examination findings.

Active and healthy sexual life with an ability to ejaculate (reported sexual activity over the last 3 months).

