## Results

In this study, 103 patients were assessed for eligibility; 8 patients did not meet the criteria and 5 patients refused to participate in the study. The remaining patients were randomly allocated into two equal groups (45 patients in each). All allocated patients were followed-up and analyzed statistically (**Figure 42**).

[figure not shown]

[figure not shown]
Figure 1: CONSORT flow chart of the enrolled patients.

[figure not shown]

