**Table 2: IPSS score of the studied groups**

	Group 1 (n=43)	Group 2 (n=41)	P value	Mean difference (95% CI)
Preoperative (0-35)	26.58±3.65	28.42±3.2	0.013*	-1.84(-3.28: -0.406)
3 months postoperative	7.14±2.99	6.68±2.43	0.446	0.456(-0.729: 1.642)
6 months postoperative	5.12±2.62	4.07±3.38	0.117	1.043(-0.265:2.352)

\*Significantly different as P value  $\leq 0.05$ , CI: Confidence interval, IPSS: International prostate symptom Score

IPSS score was significantly lower at preoperative (0-35) in group 1 than group 2 as (P value = 0.013) and was insignificantly different at (3 and 6 months) postoperative between both groups.

[figure not shown]

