**Figure 5: IIEF-5Q of the studied groups.**

**Table 4: MSHQ-EjD score of the studied groups**

	Group 1 (n=43)	Group 2 (n=41)	P value	Mean difference (95% CI)
Preoperative (1-15)	12.42±1.23	10.98±2.16	<0.001*	1.44(0.708: 2.181)
3 months postoperative	10.26±1.42	9.63±1.77	0.284	0.632(-0.544: 1.808)
6 months postoperative	10.62±1.76	10.38±2.26	0.741	0.243(-1.232: 1.717)

\*Significantly different as P value  $\leq 0.05$ , CI: Confidence interval, MSHQ-EjD: Male sexual health questionnaire – ejaculatory dysfunction short form, TTT: Treatment

MSHQ-EjD score was significantly higher at preoperative (1-15) in group 1 than group 2 (P value <0.001) and was insignificantly different at three and six months postoperative between both groups.

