**Table 7: PVR (ml) and Qmax (ml/sec) of the studied groups**

		Group 1 (n=43)	Group 2 (n=41)	P value	Mean difference (95% CI)
PVR (mL)	Preoperative	356 (250-380)	340 (289-391)	0.345	14(-20:48)
	3 months postoperative	55 (43.5-68.5)	39 (29-52)	0.003*	-13(-22: -4)
	6 months postoperative	49 (42.5-72)	34(22-47)	<0.001*	-21(-29: -12)
Qmax (mL/sec)	Preoperative	4.92±1.73	4.5±1.88	0.270	0.42(-0.334: 1.178)
	3 months postoperative	19.04±4.77	21.73±4.63	0.01*	-2.696(-4.738: -0.654)
	6 months postoperative	18.78±5.16	19.71±6.22	0.457	-0.93(-3.407: 1.55)

[figure not shown]
\*Significantly different as P value  $\leq 0.05$ , PVR: Postvoid residual, Qmax: Maximum urinary flow rate, CI: Confidence interval

PVR was insignificantly different at preoperative between both groups and was significantly higher at (3 months and 6 months) postoperative in group 1 than group 2 as (P value =0.003 and <0.001 respectively).

Qmax was significantly lower at 3 months postoperative in group 1 than group 2 as (P value =0.03) and was insignificantly different at (preoperative and 6 months postoperative) between both groups.

**Figure 12:** PVR of the studied groups.

**Figure 13:** Qmax of the studied groups.

[figure not shown]

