**Table 11: Relation between age groups and preservation of ejaculation**

	<60 years (n=24)	(60-70) years (n=46)	>70 years (n=14)	P value
After 3 months	17 (70.83%)	24 (52.17%)	2 (14.29%)	0.003*
After 6 months	17 (70.83%)	23 (50%)	2 (14.29%)	0.004*

\*Significantly different as P value  $\leq 0.05$

Preserved ejaculation after three and six months were significantly higher in patients <60 years than (60-70) and >70 years (P value  $< 0.05$ ).

**Figure 20:** Preserved ejaculation after 3 months of the studied groups.

**Figure 21:** Preserved ejaculation after 6 months of the studied groups.

[figure not shown]

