**Table 12: Relation between size of prostate groups and (preservation of ejaculation and rate of complications)**

		$\leq 60$ ml (n=51)	$>60$ ml (n=33)	P value	RR (95% CI)
Preserved ejaculation	After 3 months	25 (49.02%)	18 (54.55%)	0.621	0.9(0.59:1.37)
	After 6 months	25 (49.02%)	17 (51.52%)	0.823	0.95(0.62:1.47)
		(n=57)	(n=33)		
Intraoperative	Capsular perforation	1 (1.75%)	2 (6.06%)	0.034*	---
	Intraperitoneal bladder perforation	0 (0%)	1 (3.03%)		
	Blood transfusion	0 (0%)	3 (9.09%)		
Early postoperative	Severe irritative LUTs	5 (8.77%)	6 (18.18%)	0.488	---
	Clot retention	3 (5.26%)	3 (9.09%)		
	Stress incontinence	2 (3.51%)	1 (3.03%)		
Late postoperative	Stricture bulbar urethra	0 (0%)	3 (9.09%)	0.309	---
	Bladder neck contracture	3 (5.26%)	0 (0%)		

[figure not shown]
\*Significantly different as P value  $\leq 0.05$ , CI: Confidence interval, RR: Relative risk

Preserved ejaculation, early and late postoperative complications were insignificantly different between both groups.

[figure not shown]
Intraoperative complications were significantly lower in patients with prostate volume  $\leq 60$  ml than  $>60$  ml (P value=0.034).

**Figure 22:** Preserved ejaculation after 3 months of the studied groups.

**Figure 23:** Preserved ejaculation after 6 months of the studied groups.

[figure not shown]
**Figure 24:** Complications of the studied groups.

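### Eligibility, follow-up and row sizes do not agree: 33 of 90 men exceed the volume limit, the follow-up tables hold 84 men, and MSHQ-EjD appears to compare only men who still ejaculate

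*Combined protocol and SAP*

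**What the plan says.** - **Volume.** The inclusion criteria read "Prostate volume range: 20–60 mL". Table 6 gives ranges of 25–89 mL and 24–106 mL, and Table 12 has a column of 33 men above 60 mL.
- **Follow-up.** The Results report 103 assessed, 8 ineligible, 5 refusals and 45 men per group, then state: "All allocated patients were followed-up and analyzed statistically". Tables 2, 3, 4, 7 and 10 are headed 43 and 41. Table 11 splits the men by age, with a middle column of "60-70) years (n=46" between columns of 24 and 14.
- **MSHQ-EjD.** Table 4, headed 43/41, prints "0.632(-0.544: 1.808" at 3 months (P=0.284) and "0.243(-1.232: 1.717" at 6 months (P=0.741).
- **Late complications by volume.** Table 12 prints P=0.309, and its text concludes "early and late postoperative complications were insignificantly different between both groups". The Statistical analysis section sets a two-sided 0.05 threshold and names the chi-square test, or Fisher's exact test where appropriate.
- **Perforation.** Capsular or bladder perforation during surgery is an exclusion criterion. Capsular perforation is also listed under Intra-operative Evaluation, and Table 9 reports both types as complications.

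**The concern.** A reader needs to know which men the results describe and how many stand behind each row. Over a third of the randomised men lie outside a stated entry limit. Table 12 pools the arms, so the treatment effect within the limit cannot be read off. The completeness sentence contradicts the tables.

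The row-size problem goes beyond labelling. Ejaculation is one of three functions named in the aim. If its questionnaire is compared only in men who still ejaculate, roughly four fifths of one arm is set against one fifth of the other, selected by something the operation itself affects. Finding no difference between those subsets says little about the operations. Separately, an exclusion that can arise only during surgery, and that is also an outcome, would bias the comparison if applied after allocation.

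**Working it through.** **1. Counts.** 103 − 8 − 5 = 90 = 45 + 45, so the stated flow reproduces. Table 12's complication rows give 57 + 33 = 90, hence 33/90 = 36.7% above 60 mL. Follow-up: 43 + 41 = 84; Table 11, 24 + 46 + 14 = 84; Table 12's ejaculation rows, 51 + 33 = 84. Six men are absent, 2 in Group 1 and 4 in Group 2. If 33 is right in both blocks of Table 12, all six are at or below 60 mL (57 − 51).

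**2. Row sizes.** From the printed differences and SDs: CI = d ± t(0.975, n1+n2−2) × sp × √(1/n1 + 1/n2), with sp² = [(n1−1)s1² + (n2−1)s2²]/(n1+n2−2). MSHQ-EjD at 3 months with 35/8: sp = √[(34×1.42² + 7×1.77²)/41] = 1.486; SE = 0.582; t = 2.02; half-width 1.176.

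| Row | Printed | At 43/41 | At the size that fits |
|---|---|---|---|
| MSHQ-EjD 3 mo | −0.544 to 1.808, P 0.284 | −0.063 to 1.327, P 0.074 | 35/8: −0.544 to 1.808, P 0.284 |
| MSHQ-EjD 6 mo | −1.232 to 1.717, P 0.741 | −0.634 to 1.120, P 0.583 | 34/8: −1.232 to 1.718, P 0.741 |
| IPSS preop | −3.28 to −0.406, P 0.013 | −3.333 to −0.347, P 0.016 | 45/45: −3.278 to −0.402, P 0.013 |
| Qmax 3 mo | −4.738 to −0.654, P 0.01 | −4.738 to −0.654, P 0.010 | 43/41 |

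Table 10 gives 35 and 8 men with preserved ejaculation at 3 months, and 34 and 8 at 6 months. Semen volume behaves the same way. At 3 months 35/8 gives an upper limit of 0.955 and P=0.225 (printed 0.953 and 0.223), whereas 43/41 would give P=0.018. At 6 months 34/8 gives P=0.796 (printed 0.797), against 0.633 at 43/41. The preoperative IIEF-5, MSHQ-EjD and Qmax rows also fit 45/45.

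**3. Table 12 complication P values.** Uncorrected chi-square with a no-event column, treating events as distinct men:

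- Intra-operative: 8.683 on 3 df, P=0.0338 (printed 0.034).
- Early: 2.425 on 3 df, P=0.4889 (printed 0.488).
- Late, strictures/contractures/none [0, 3, 54] vs [3, 0, 30]: 6.951 on 2 df, P=0.0309 (printed 0.309). At 51/33, P=0.037.
- Late, exact (Fisher-Freeman-Halton): 0.049 at 57/33, 0.031 at 51/33.
- Any late event, 3/57 vs 3/33: Fisher P=0.665.

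**4. Table 9 P values.** Late 0.699 fits 45/45 (0.6997), not the printed 43/41 (0.662). Early 0.506 fits only without the bladder neck contracture row (0.5063; with it, 0.578). Table 12's early block also lacks that row.

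**5. Perforation.** Table 9 has 1 event against 3 (capsular 1 and 2, bladder 0 and 1). Table 12 puts three of the four above 60 mL, a stratum of 33 in both blocks. On those counts nobody there was removed.

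**6. Preserved ejaculation at 6 months.**

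- Observed: (34/43)/(8/41) = 4.05 (95% CI 2.14 to 7.69). Table 10's printed 15.58, labelled RR, is the odds ratio (34×33)/(9×8).
- All 90, worst case for Group 1 (34/45 vs 12/45): 2.83 (1.70 to 4.73). Missing as failure (34/45 vs 8/45): 4.25 (2.22 to 8.14). Best case (36/45 vs 8/45): 4.50 (2.36 to 8.58).
- Followed men at or below 60 mL: 25 preserved and 26 not. Group 1 can hold 17 to 25 of the former and 0 to 9 of the latter, which gives 90 splits. The least favourable is 17/26 vs 8/25, RR 2.04, Fisher P=0.025, the largest P over all splits.

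**The case against.** The flow chart is not reproduced and may explain the six losses; only the conflict between sentence and tables is demonstrable. The men above 60 mL are shown openly in Tables 6 and 12; what is absent is any statement that they breach the criterion. Row sizes inferred from interval widths are not unique. Here, though, the limits and P values agree closely at counts that Table 10 prints. There may also be good reason to score ejaculation only in men who ejaculate. That would justify a labelled descriptive subset, but not a 43/41 header or a between-arm conclusion.

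On the late P value, the expected event counts are below 5, so the plan might call for an exact test, which gives only 0.049 at 57/33. It rests on six events in an unplanned subgroup. That limits its weight but does not rescue 0.309.

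Some stronger readings are tempting and unsupported:

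- *The losses or ineligible men undermine the preserved-ejaculation result.* Every bound above favours Group 1. The losses did not shrink an effect of 15.58, which is an odds ratio.
- *The six men were dropped for perforation.* Three of the four events lie in a stratum that loses nobody.
- *The 3-month Qmax finding hangs on the missing men.* It loses significance (−1.79, −4.34 to 0.77) if all six are set to their arm's preoperative mean. That is a severe stress test, not evidence about those men. The 6-month IIEF-5 difference survives the same rule (2.06, 0.81 to 3.30).
- *Large prostates have more late complications.* The types differ (all three strictures above 60 mL, all three contractures at or below), but the totals are 3 and 3.

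**Conclusion.** The point holds, mainly as a set of reporting and analysis errors. The completeness sentence is wrong against the document's own tables. Of the randomised men, 37% exceed the volume limit without being declared as deviations. Several row sizes are wrong, and the Table 12 sentence on late complications does not follow from its counts at 0.05.

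The most consequential item is the apparent restriction of postoperative MSHQ-EjD and semen volume to 35 or 34 men against 8. It rests on rounded SDs and a pooled-variance t interval. The direction of the preserved-ejaculation result is secure. Its size within the volume limit is not reported; the floor of 2.04 assumes that Table 12's 51/33 margins are right. Whether the perforation exclusion was ever applied at or below 60 mL cannot be told.

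**What to change.** 1. Correct the flow sentence to 90 randomised and 84 in the follow-up tables, with reasons by arm.
2. Print the true n on every row. Label the MSHQ-EjD and semen rows as restricted to men with preserved ejaculation and not a randomised comparison. Add MSHQ-EjD by arm in all followed men where scores exist, with a stated rule for men without ejaculation, or withdraw the between-arm conclusion.
3. Use one denominator for late events in Tables 9 and 12, recompute Table 12's late P with an exact test and correct its sentence. Reconcile the early contracture row, and relabel Table 10's odds ratios.
4. Declare the 33 men as volume deviations by arm, or restate the population described. Keep the as-randomised analysis as main and add a by-arm sensitivity analysis at or below 60 mL (57 randomised, 51 followed).
5. Reconcile the perforation exclusion with its use as an outcome: say whether and to whom it was applied, and keep all randomised men in the analysis.
6. Add a missing-data sensitivity analysis with one stated rule for both arms, presented as a stress test.

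The cost is re-tabulation of existing data and corrected text. The restricted analysis will have wider intervals and may be less conclusive, and the exact late P will stay near 0.05 whichever denominator is right.

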**-Exclusion criteria:**

History of prostate, bladder or urethral surgery.

Neurogenic bladder.

Untreated active urinary tract infection (UTI).

Urethral stricture disease.

Biopsy confirmed prostate cancer.

Bleeding diathesis.

Capsular or bladder perforation during surgery.

**-Ethical consideration:**

All patients will be fully informed about the operations, and written informed consents will be obtained.

Approval from ethical committee of Sohag faculty of medicine will be obtained.

**-Methods of the study:**

**Pre-operative Evaluation:**

- History, which includes IPSS, the International Index of Erectile Function 5 items Questionnaire (IIEF-5Q), and the Male Sexual Health Questionnaire-Ejaculatory Dysfunction Short Form (MSHQ-EjD).

- Physical examination, which includes a digital rectal examination.

- A pre-operative lab study, which includes urine analysis, hemoglobin, creatinine, and PSA levels.

-Trans abdominal ultrasonography to determine prostate volume and post void residual (PVR) urine volume.

- Uro-flow-metry (Qmax).

**Surgical Technique:**

Cystoscopy will be conducted under spinal anaesthesia with a 30° telescope and the patient in dorsal lithotomy posture. Eligible patients will be randomly assigned to one of two groups with double blind evaluation. Group 1 will have ejaculatory preserving TURP, whereas Group 2 will

have traditional TURP. Randomization will be done by computer programming such as SAS. The Operators will be the supervisors of the principle investigator.

All procedures will be carried out with bipolar-flow 26 Fr bipolar resectoscopes (Karl-Storz, Germany) configured for resection in 0.9% saline solution and cut/coagulation set at 130/70 W.

In Group 1, resection of lateral lobes to the capsule and the ventral side to the level of the verumontanum with avoidance of paracollicular digging. Circular resection of the internal bladder neck will be done. Then the next step will be apical resection utilizing the colliculus seminalis as a distal resection border and maintaining a 1 cm safety area for preservation of ejaculation.

In Group 2, the whole adenoma tissue, including the tissue in front of the verumontanum and bladder neck, will be removed to the prostatic capsule.

After full hemostasis, a 20 Fr three-way catheter will be placed into the bladder, traction will be performed, and the bladder will be irrigated with 0.9% saline postoperatively until clear effluent is seen.

The patient will be discharged from the hospital on the next postoperative day. Sexual activity will be prohibited for 6 weeks following the intervention.

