**Statistical analysis:**

Statistical analysis was done by SPSS v26 (IBM Inc., Chicago, IL, USA). Shapiro-Wilks test and histograms were used to evaluate the normality of the distribution of data. Quantitative parametric variables were presented as mean and standard deviation (SD) and compared between the two groups utilizing unpaired Student's T- test. Quantitative non-parametric data were presented as median and interquartile range (IQR) and were analyzed by Mann-Whitney test. Qualitative variables were presented as frequency and percentage and were analyzed utilizing the Chi-square test or Fisher's exact test when appropriate. A two tailed P value  $< 0.05$  was considered statistically significant

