**Table 6: Prostate volume (ml) of the studied groups**

Prostate volume (ml)	Group 1 (n=45)	Group 2 (n=45)	P value	Mean difference (95% CI)
	Mean $\pm$ SD	53.69 $\pm$ 17.71		-3.42(-11.15: 4.31)
	Range	25 – 89	24 – 106	

\*Significantly different as P value  $\leq$ 0.05, PVR: Postvoid residual, Qmax: Maximum urinary flow rate, CI: Confidence interval

Prostate volume was insignificantly different between both groups.

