**Table 8: Intraoperative factors of the studied groups**

		Group 1 (n=45)	Group 2 (n=45)	P value	Mean difference or RR (95% CI)
Operative time (min)	Mean <math>\pm</math> SD	33.51 $\pm$ 11.49	40.53 $\pm$ 14.64	0.013*	-3.42(-11.15: 4.31)
	Range	15 – 60	18 – 75		
Blood transfusion		1 (2.22%)	2 (4.44%)	1	0.49(0.04:5.59)

[figure not shown]
\*Significantly different as P value  $\leq$ 0.05, CI: Confidence interval, RR: Relative risk

Operative time was significantly lower in group 1 than group 2 as (P value =0.013).

Blood transfusion was insignificantly different between both groups.

**Figure 14:** Operative time of the studied groups.

[figure not shown]
**Figure 15:** Blood transfusion of the studied groups.

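### Operative time is compared without prostate volume, which costs precision and leaves in a small chance imbalance; the difference printed in Table 8 belongs to another row; operator is an unreported secondary factor

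*Combined protocol and SAP*

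**What the plan says.** All places are in the combined protocol and SAP.

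- **Analysis.** The Statistical analysis section lists only two-group tests. Normally distributed quantitative variables are "compared between the two groups utilizing unpaired Student's T- test". No covariate-adjusted or stratified method is named, and no table reports one.
- **Operative time.** Table 8 gives 33.51 ± 11.49 min in Group 1 and 40.53 ± 14.64 min in Group 2. The text below it reads "Operative time was significantly lower in group 1 than group 2 as (P value =0.013". The difference printed in that row is -3.42 (-11.15 to 4.31).
- **Prostate volume.** It is measured by ultrasound before surgery (Pre-operative Evaluation). Table 6 is headed 45 men per arm, prints a difference of -3.42 (-11.15 to 4.31) and concludes "Prostate volume was insignificantly different between both groups".
- **Allocation.** Under Surgical Technique: "Eligible patients will be randomly assigned to one of two groups with double blind evaluation", and "Randomization will be done by computer programming such as SAS". Neither strata nor blocks are mentioned. The Results state that patients were "randomly allocated into two equal groups (45 patients in each").
- **Operators.** The same section says "The Operators will be the supervisors of the principle investigator". It does not give their number, their experience or their cases per arm.

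**The concern.** Gland size is a natural predictor of how long a resection takes, and volumes here ran from 24 to 106 mL (Table 6). A non-significant difference in volume between arms does not remove its influence on time. The small imbalance stays in the estimate, and the spread due to volume stays in the standard error. Volume is fixed before surgery and already collected, so leaving it out gives away precision for nothing.

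The operator could act in the same way if operators differ in speed and were not spread evenly over the arms. The documents give no count from which to judge this.

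At stake are the size and interval of one intraoperative outcome. The row needs correcting anyway, because its printed interval includes zero beside a P value of 0.013.

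**Working it through.** **Step 1. Reproduce the plan's P value.** Inputs are the Table 8 means and SDs, with 45 men per arm.

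- Difference: 33.51 - 40.53 = -7.02 min.
- Pooled SD: √[(11.49² + 14.64²)/2] = 13.16 min.
- SE: 13.16 × √(2/45) = 2.77 min, so t = -2.53 on 88 df and P = 0.0132. The stated 0.013 reproduces.
- 95% CI: -7.02 ± 5.51, that is -12.53 to -1.51.

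**Step 2. Check the printed difference.** The Table 8 figures match the Table 6 volume row digit for digit. Half-width (4.31 + 11.15)/2 = 7.73 gives SE 3.89, so -3.42 would imply P = 0.38. It cannot belong with P 0.013 or with the Table 8 means.

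**Step 3. Recover the volume inputs.** In the text available, one arm's mean and SD in Table 6 cannot be read, so the printed difference and interval are used.

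- Pooled volume SD: 3.89/√(2/45) = 18.45 mL, consistent with the one readable SD, 17.71.
- Direction: the age row shows the convention is Group 1 minus Group 2 (62.76 - 65.58 = -2.82). So -3.42 mL is taken to mean smaller glands in Group 1.

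**Step 4. Adjust for volume.** The documents give no volume-time correlation r, so a range is assumed for the within-arm value.

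- Slope b = r × 13.16/18.45.
- Adjusted difference = -7.02 - b × (-3.42).
- SE = 13.16 × √(1 - r²) × √(88/87) × √[2/45 + 3.42²/(88 × 18.45²)], on 87 df.

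| Assumed r | b (min/mL) | Due to volume (min) | Adjusted difference (95% CI) | Half-width | P |
|---|---|---|---|---|---|
| 0 | 0 | 0 | -7.02 (-12.59 to -1.45) | 5.57 | 0.014 |
| 0.3 | 0.214 | 0.73 | -6.29 (-11.60 to -0.97) | 5.31 | 0.021 |
| 0.5 | 0.357 | 1.22 | -5.80 (-10.62 to -0.98) | 4.82 | 0.019 |
| 0.7 | 0.499 | 1.71 | -5.31 (-9.29 to -1.33) | 3.98 | 0.009 |
| 0.9 | 0.642 | 2.20 | -4.82 (-7.25 to -2.40) | 2.43 | <0.001 |

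For r of 0.3 to 0.7 the estimate shrinks by 0.73/7.02 = 10% to 1.71/7.02 = 24%.

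**Step 5. Could gland size explain the whole difference?** That needs a slope of 7.02/3.42 = 2.05 min per mL. The largest slope the SDs allow (r = 1) is 13.16/18.45 = 0.71, which accounts for 0.71 × 3.42 = 2.4 min, or 35%.

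**Step 6. Operator.** No operator data are given, so this step is illustrative. Assume two operators sharing cases equally, with allocation independent of operator.

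- The between-arm difference in one operator's share has SE √(0.25 × 2/45) = 0.105, so its 95% range is about ±0.21.
- Shift in operative time = difference in mean time between operators × imbalance in share. With an assumed 5 to 15 min and 0.10 to 0.20, it runs from 5 × 0.10 = 0.5 to 15 × 0.20 = 3.0 min, in either direction.
- Preserved ejaculation at 6 months (Table 10) is 34/43 = 79.07% against 8/41 = 19.51%, a gap of 59.6 points. With an imbalance of 0.20, even operators with 0% and 100% preservation would shift the gap by only 0.20 × 100 = 20 points.

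**The case against.** The strongest reply is that allocation was individually randomised. Operator and gland size are then chance imbalances, not systematic confounders, and the unadjusted t test is a valid analysis. That stands. It is also fair that adjustment does not change the conclusion, that the gain is slight at r = 0.3 (half-width 5.5 to 5.3 min), and that operative time is not among the stated aims of voiding, erectile function and ejaculation.

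What the reply does not remove is the avoidable loss of precision. Nor can balance be presumed in one trial of 90: preoperative IPSS (P 0.013), MSHQ-EjD (P <0.001) and total PSA (P 0.001) all differ between the arms.

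A reader might go further and infer that the shorter operative time is a mixture of technique, surgeon and gland size. The documents do not support this.

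- More than one operator is inferred from a single plural.
- Nothing says that operators were tied to an arm.
- A split such as 65% against 35% for one operator would, under the Step 6 assumptions, lie 0.30/0.105 = 2.85 SE from balance (P about 0.004). Chance alone is therefore an unlikely source.
- The text says only that operative time was lower in Group 1. No 7-minute figure is printed.

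**Conclusion.** The point holds as one of precision and reporting. The unadjusted comparison is valid, but it omits a measured preoperative covariate. For assumed r of 0.3 to 0.7, the difference moves from -7.02 to between -6.3 and -5.3 min, the half-width falls from 5.5 to between 5.3 and 4.0 min, and P stays below 0.05. These figures rest on the assumed correlation and on a volume SD and direction recovered from the printed interval and sign convention. At the low end of r the P value rises slightly (0.021 against 0.013), because the estimate moves more than its error shrinks.

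The firmest error is the Table 8 difference, which duplicates the volume row and contradicts its own P value.

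The operator question is a gap in reporting. A shift of 0.5 to 3.0 min either way is conceivable under the stated assumptions; no actual confounding is shown, and the preserved-ejaculation result is not threatened. It would be wrong to infer that adjustment overturns the operative-time result.

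**What to change.** 1. In Table 8, replace the printed operative-time difference with -7.02 (95% CI -12.53 to -1.51), after checking it against the patient data.
2. Fit a linear model of operative time on arm and preoperative prostate volume. Report the adjusted difference and 95% CI beside the unadjusted one, labelled as added after the results were known, and describe the model in the Statistical analysis section.
3. State how many operators there were and whether allocation took account of them. If the operator was recorded, give cases per operator by arm and add operator to the model as a sensitivity analysis. If it was not recorded, say so as a limitation.

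Items 1 and 2 use data already collected. The model costs one degree of freedom for volume and one or a few for operator. If volume turned out unrelated to time, the half-width would widen only from 5.51 to 5.57 min.
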